13.2 Publication and Dissemination policy

Results of this research project will be shared at three levels. At the district and community level, during meetings headed by the District Health Management Team, such as at the PHC (primary health care) meeting where - in addition to the District Health Management Team - also representatives from all health centres are present. At the national level, at the national research symposium of the Ministry of Health, and at the international level through presentations at conferences (especially at the conferences of the International AIDS Society) and publications in peer-reviewed journals. The current version of the ICMJE recommendations⁴⁰ is applicable regarding authorship eligibility and the use of professional writers is not intended. Before trial start, PEBRA study will be registered in the trial register 'clinicaltrials.gov'.

13.3 Compensation

13.3.1 Study participants

Participation in this study is not anticipated to cause any substantial additional risk or cost to the participant. Therefore, we will not pay compensation to the participants.

13.3.2 Study personnel

As the incentive for PEs currently differs, we will ensure that all involved PEs receive a minimum stipend per month. They will receive an android-based tablet with the two applications (PEBRAApp & KoboToolbox) installed, a simcard, and regular AirTime (prepaid money for calling and for data usage) for the duties of the study.

14 WITHDRAWAL OF PARTICIPANTS AND DISCONTINUATION OF TRIAL

14.1 Withdrawal

The study participant has the right to withdraw from the study at any time without giving reasons. In case of withdrawal, only data collected until the time of withdrawal will be used for research purposes (fully anonymized, identifier removed). Discontinued participants will not be replaced. A participant or cluster (if applicable) can be withdrawn from the study by the Principal Investigator for the following reasons:

1. withdrawal of informed consent
2. ethical concerns
3. major violation of the study protocol
4. intolerable side-effects, adverse events
5. any conditions that might jeopardize the patient's health if they were to continue in the study

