5.1 Primary endpoint

In care with documented viral suppression at 12 months, defined as the proportion of participants in care with a documented VL <20 copies/mL 12 months (range: 9 – 15 months) after enrolment out of all participants enrolled

- i. *Rational for VL suppression level at 20 copies/mL: VL determination will be done on COBAS TaqMan® HIV-1 Test, v2.0 (Roche Diagnostics) using plasma, and has a reliable lower limit of detection of 20 copies/mL*
- ii. *Definition of "in care": at least one ART visit in the defined window*
 - I. *Including participants who transferred out to any other health facility with known outcome (documented proof of follow-up visit or laboratory test)*
 - II. *Excluding participants who died (all-cause), were lost to follow-up (LT FU), or were known defaulters/refusers, i.e. were more than 2 months late for ART refill with a reason available (e.g. currently no money for clinic-visit, busy working in South Africa, etc.)*
- iii. *The study will use VL results from routine VL monitoring. To synchronize routine VL monitoring and study VL monitoring, study staff will help ensure each site has the capacity to collect these samples and will support existing systems that help to provide results back to sites. VLs will only be performed on individuals who return for visits and no tracking will be performed by the study staff to obtain VLs.*

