11.2 Analyses

All analyses will be done using R (the R Foundation for Statistical Computing) or Stata (version 14, Stata Corporation) in Lesotho. For all tests, we will use 2-sided p-values with alpha 0.05 level of significance. A detailed data analysis plan will be developed separately.

Clusters will be set as unit of randomization (stratified by district), whereas individuals are set as unit of analysis. Multilevel random effects models will be used to analyze the data. We will present a CONSORT flowchart of the participants, including screening, enrollment and follow-up. The following analysis sets will be used in this trial:

1. Intention-to-treat (ITT) set: All study participants will be evaluated according to cluster assignment at randomization
2. Per-protocol (PP) set: This set includes all participants who completed the study without a major protocol deviation

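### The data cut-off in section 14.1 is not limited to consent withdrawal, so an investigator-initiated withdrawal can discard a 12-month outcome that routine records would hold and undermine the intention-to-treat analysis

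*Combined protocol and SAP*

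**What the plan says.** Section 14.1 opens with the participant's right to leave the study and continues: "In case of withdrawal, only data collected until the time of withdrawal will be used for research purposes". After noting that discontinued participants are not replaced, it adds: "A participant or cluster (if applicable) can be withdrawn from the study by the Principal Investigator for the following reasons". Five reasons follow. Withdrawal of consent is the first. The others include ethical concerns, "major violation of the study protocol" and "intolerable side-effects, adverse events".

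Section 11.2 defines the ITT set without any exception for withdrawal: "All study participants will be evaluated according to cluster assignment at randomization". Protocol deviations are dealt with in a separate per-protocol set: "This set includes all participants who completed the study without a major protocol deviation".

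The primary endpoint in section 5.1 requires a documented viral load (VL) below 20 copies/mL, assessed at "12 months (range: 9 – 15 months) after enrolment out of all participants enrolled". Its source is routine care: "The study will use VL results from routine VL monitoring". Section 12.1 likewise takes follow-up data from routine facility records. Section 4.3.8 accepts that participants and staff cannot be fully blinded.

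No section says how a participant or clinic withdrawn by the investigator is scored in the primary analysis.

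**The concern.** Section 14.1 lists consent withdrawal as only one kind of withdrawal, so its cut-off sentence, taken at its word, reaches the other kinds too. The primary outcome exists only from month 9. Any earlier withdrawal by the investigator therefore makes that outcome unusable, whatever the routine record later shows.

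Three things make this matter:

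- The decision to withdraw is made after randomisation by people who know the allocation, and section 14.1 does not define a major violation. The intervention arm has more procedures that can be violated (for example the scheduled preference assessments in section 4.3.5), so withdrawals could differ by arm.
- A major deviation is meant to affect only the per-protocol set. Under section 14.1 the same event could also cost the ITT analysis its outcome.
- The loss is avoidable. The VL is a routine measurement, and people in a clinic withdrawn for a violation have not themselves withdrawn consent to data collection.

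The safety endpoint (section 5.3) and mortality (section 5.2) share the problem: someone withdrawn for an adverse event would stop contributing later events.

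**Working it through.** **Inputs.** From section 11.1: 300 participants, 20 clinics, 10 per arm, 15 per clinic, control rate 70%, a 20% increase (read as 70% to 90%), ICC 0.05, design effect 1.7, power 90%. From section 11.2: two-sided alpha 0.05. The numbers withdrawn below are assumptions.

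**Step 1: the plan's own figure.**
- Design effect = 1 + (15 − 1) × 0.05 = 1.70.
- Effective n per arm = 150 / 1.7 = 88.2.
- Power (pooled z) = Φ{[d√n − 1.96√(2p̄(1 − p̄))] / √(p₁(1 − p₁) + p₂(1 − p₂))}. With d = 0.20 and p̄ = 0.80 this is Φ{(1.879 − 1.109) / 0.548} = 92.0%.
- A non-central t with 18 cluster degrees of freedom gives 90.0%. The stated 90% is reproduced.
- A relative 20% increase (70% to 84%) would give only 60%, so the absolute reading is the one the plan used.
- Planned odds ratio = (0.90/0.10) / (0.70/0.30) = 3.86.

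**Step 2: how the sections combine.** Section 14.1 (literal) means no data after withdrawal are used. Section 5.1 means everyone enrolled is in the denominator and success needs a documented VL. Section 11.2 means all participants are analysed by assignment. Together, a person withdrawn before month 9 stays in the denominator without a usable VL and counts as not suppressed.

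**Step 3: one clinic of 15 withdrawn before its 12-month VLs and scored as failures.**
- Intervention clinic: 0.90 × 135/150 = 0.81. The difference falls from 20 to 11 points and the crude odds ratio is (0.81/0.19) / (0.70/0.30) = 1.83. Power by the Step 1 formula is 39.6%, against 92.0% before.
- Control clinic: 0.70 × 135/150 = 0.63. The difference rises to 27 points and the odds ratio is 5.29. With no true effect (70% in both arms) this alone creates a 7-point difference, odds ratio 1.37.

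These power figures keep the design effect at 1.7. A clinic with no successes would add between-clinic variation, so they are approximate.

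**Step 4: individual withdrawals, intervention arm only, unrelated to outcome, scored as failures.**

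| Withdrawn of 150 | Observed rate | Difference from 70% | Power (pooled z) |
|---|---|---|---|
| 5 | 0.90 × 145/150 = 87.0% | 17.0 points | 79% |
| 8 | 0.90 × 142/150 = 85.2% | 15.2 points | 68% |
| 15 | 0.90 × 135/150 = 81.0% | 11.0 points | 40% |

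**Step 5: exclusion instead, for comparison only.** The documents do not state this route. Dropping one clinic leaves power at about 90–91% (pooled z), so any harm would be selection bias. With no true effect, dropping 5, 8 or 15 non-suppressed intervention participants gives 105/145 = 72.4%, 105/142 = 73.9% or 105/135 = 77.8%. Those are false differences of 2.4, 3.9 and 7.8 points.

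**The case against.** The best defence is that the cut-off was only ever meant for consent withdrawal. In section 14.1 it directly follows the participant's own right to leave and comes before the list of investigator reasons. Section 13.1 uses the same rule immediately after the right to withdraw consent. This is a fair reading of intent, but the wording in section 14.1 does not carry the limit. If it was intended, the fix only makes it explicit.

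A reader might infer that all data from withdrawn participants are thrown away. They are not: data collected before withdrawal are kept.

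A reader might also infer that withdrawn people or clinics leave the analysis, so that ITT is defeated. The documents do not support that. The ITT set has no withdrawal exception and the denominator is everyone enrolled, so the likely result is misclassification as failure. Exclusion would need a further decision that is not written anywhere.

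The one-clinic case is an extreme. Section 14.1 qualifies the cluster option, section 12.3 expects no major adverse effects, and intervention participants may return to facility-based care at any time. Those points make large numbers less likely. They do not settle how any withdrawal is scored.

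Finally, section 5.1 has study staff supporting sites' capacity to collect VL samples. A withdrawn clinic might lose that help, so better wording may not secure every VL. This stands, and it is why a scoring rule for a missing VL is also needed.

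**Conclusion.** The point holds as an unresolved conflict between section 14.1 and sections 5.1 and 11.2. On its literal wording, section 14.1 lets an unblinded, post-randomisation decision remove a primary outcome that routine records would hold, and the rest of the plan then most likely counts that person as not suppressed. This can undermine the ITT analysis. It does not abolish it.

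The size depends entirely on how many are withdrawn, in which arm and when, and the documents give no figure. If one clinic of 15 is withdrawn before its 12-month VLs and scored as failures, that arm moves by 9 points (90% to 81%) or 7 points (70% to 63%) against the planned 20. Five individual withdrawals in the intervention arm would cost 3 points. If nobody is withdrawn by the investigator before the window, or if the cut-off is applied only to consent, there is no effect.

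**What to change.** In section 14.1:

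- Limit the data cut-off to withdrawal of consent, or to cases where the consent itself is found invalid or an ethics concern bars data use.
- For any other investigator-initiated withdrawal, state that only study procedures stop. Record-based outcomes continue to be collected through month 15 and are analysed in the allocated arm.

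In section 11.2 or the separate analysis plan:

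- State that every randomised clinic stays in the ITT set and that protocol violations are handled only in the per-protocol set.
- State that a VL still missing after withdrawal counts under the primary endpoint definition as not documented suppressed, with a sensitivity analysis that varies this scoring by arm.
- Report investigator-initiated withdrawals by arm, clinic, reason and timing.

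The cost is a short wording change with no added visits. A withdrawn clinic may still yield fewer VLs if it loses sampling support. Nothing here changes when treatment or the intervention is stopped.

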14.2 Discontinuation of the entire study

The Sponsor/Principal Investigator may terminate the study prematurely according to certain circumstances, for example:

1. ethical concerns
2. insufficient participant recruitment
3. when the safety of the participants is doubtful or at risk
4. alterations in accepted clinical practice that make the continuation of a clinical trial unwise

The Sponsor/Principal Investigator would provide written notice and instructions for study termination submitted at a reasonable time to all involved stakeholders.

15 FUNDING SOURCES AND ROLE OF THE FUNDING SOURCES

This trial is predominantly funded by a CIPHER grant from the International AIDS Society, obtained by AA. AA receives his salary through a grant from the MD-PhD programme of the Swiss National Science Foundation (Grant number 323530_177576). Further funding came from a grant of the Stiftung für Infektiologie beider Basel and two grants from the Swiss National Science Foundation (Grant Number IZ07Z0_160876/1 and Grant Number PCEFP3_181355), all obtained by NDL. The Swiss TPH acts as sponsor of the study. The study is embedded in the SolidarMed country programme and thus benefits from logistics and human resources from SolidarMed Lesotho. The same applies for Sentebale Lesotho.

All funding sources have no role in the design of the study, and will not be involved in data collection, data analysis, interpretation of the results and writing of the manuscript.

16 STUDY TIMELINE

We expect recruitment to start August/September 2019 and a total study duration of approximately 18 months. Figure 3 illustrates the time-line of PEBRA study, incl. preparation and pilot phase. We anticipate a recruitment period of 4-5 months.

FIGURE 3. Time-line of PEBRA study incl. preparation and pilot phase

March 2019	15.03.19:(Submission(of(study(protocol(to(ethics(committees 30.03.19:(PEBRA/Workshop(1 31.03.19:(PEBRA/Workshop(2 Registration(on(cclinicaltrials.gov
April 2019&	Finalizing(PEBRAApp(and(KoboToolbox Setting(up(PEBRA(form(on(VL(platform Acquisition(and(setting/up/of/1/study/tablet Training(of/1/peerEducator(for/pilot/trial
May 2019	After/feedback/from/ethics/committees:(Start%Pilot%Trial
June 2019	Training(of/all/other/peer/Educators Training/information/at/all/(involved/health/centers/at/DHMTs
July 2019	End%Pilot%Trial Analysis(of/pilot/trial/outcomes If/needed:(Submission(of/study(protocol/amendment(for/main/trial
August 2019	Start%PEBRA%Trial
October 2020	End%PEBRA%Trial Analysis,(writing/of/report,(dissemination/of/results

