secondary endpoints	
a) Adherence to ART at 3 months, 6 months and 12 months after enrolmentb) Quality of Life at 6 months and 12 months after enrolmentc) Perceived quality of ART Care / patient service satisfaction at 6 months and 12 months after enrolmentd) Engagement in care at 6 monthse) Alternative viral suppression level at 12 monthsf) Engagement in care at 12 monthsg) All-cause mortality at 6 and 12 monthsh) LTFU at 6 and 12 monthsi) Transfer out at 6 and 12 months
sample size & statistical considerations	
An overall target sample size of 300 AYPLHIV in 20 clusters (10 per arm) will provide us 90% power (design effect of 1.7) to detect a 20% increase of viral suppression in the intervention group, assuming a type 1 error of 0.05, and an intra-cluster correlation coefficient (ICC) of 0.05.
 
Clusters, i.e. clinics, will be set as unit of randomization (stratified by district), whereas individuals are set as unit of analysis. The primary analysis will use multi-level logistic regression models (on the intention-to-treat set) including clinic as random effect to assess the difference between viral suppression rate in the intervention versus control arm, adjusted for the pre-specified randomization stratification factor, baseline VL, and relevant baseline factors that may be randomly unbalanced between intervention and control clusters. All results will primarily be presented as odds ratios and their respective 95% confidence intervals.

recruitment & study duration	We expect recruitment to start August/September 2019 and a total study duration of approximately 18 months. We anticipate a recruitment period of 4-5 months. A pilot trial, assessing PEBRA model at one health facility, will form the basis for the main trial.
GCP statement	This study will be conducted in compliance with the protocol, the current version of the Declaration of Helsinki, the ICH-GCP or ISO EN 14155 (as far as applicable) as well as all national legal and regulatory requirements.

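### Figure 3 ends the trial in October 2020, before the last participants can reach month 12 on the protocol's own recruitment and follow-up figures

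*Combined protocol and SAP*

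**What the plan says.** Section 16 gives the calendar in words: "We expect recruitment to start August/September 2019 and a total study duration of approximately 18 months", followed by "We anticipate a recruitment period of 4-5 months". The synopsis repeats "a total study duration of approximately 18 months" alongside the same recruitment start and length. Neither place says which event the 18 months are counted from.

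Figure 3, in the same section, gives the calendar by month. It also covers preparation and the pilot. May 2019 carries "Start%Pilot%Trial", August 2019 carries "Start%PEBRA%Trial", and October 2020 carries "End%PEBRA%Trial", with analysis, report writing and dissemination in the same row. (The percent signs come from text extraction; the months and milestones are legible.)

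The endpoints are set in participant time. Section 5.1 measures the primary endpoint at "12 months (range: 9 – 15 months) after enrolment out of all participants enrolled". Section 5.3 counts SAEs over the 12 months after enrolment and gives no window. The note to Table 1 fixes a month at 30 days.

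**The concern.** The recruitment period and the 12-month follow-up add up to more time than Figure 3 allows between its start and its end. In the text available, October 2020 is the only calendar date given for the end of the main trial, and analysis is placed beside it.

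If data capture stopped then, two things would follow for later enrolees:

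- **Safety endpoint.** It needs a full 12 months of observation and has no window, so it would be incomplete.
- **Primary endpoint.** It needs a documented VL and keeps everyone enrolled in the denominator. A suppressed VL drawn later in the window would count as a failure.

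**Working it through.** **Inputs.** Recruitment start S: August/September 2019 (section 16), taken as 1 August to 30 September. Recruitment length R: 4-5 months, or 120-150 days (section 16). Primary endpoint at day 360, window day 270 to day 450 (section 5.1, 30-day months). Figure 3: start August 2019, end October 2020, read as 31 October 2020, which is the reading most favourable to the plan.

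**Step 1: can Figure 3's end date be reproduced?** Time needed to the last month 12 is 4-5 + 12 = 16-17 months. From 1 August 2019 to 31 October 2020 is 457 days (15.2 months); from 31 August 2019 it is 427 days (14.2 months). It cannot.

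**Step 2: dates for the last participant.** Last day 360 = S + R + 360; last day 450 = S + R + 450.

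| Start S | R (days) | Last day 360 | Last day 450 | Last enrolee's day on 31 Oct 2020 |
|---|---|---|---|---|
| 1 Aug 2019 | 120 | 23 Nov 2020 | 21 Feb 2021 | 337 |
| 1 Aug 2019 | 150 | 23 Dec 2020 | 23 Mar 2021 | 307 |
| 31 Aug 2019 | 120 | 23 Dec 2020 | 23 Mar 2021 | 307 |
| 31 Aug 2019 | 150 | 22 Jan 2021 | 22 Apr 2021 | 277 |
| 30 Sep 2019 | 120 | 22 Jan 2021 | 22 Apr 2021 | 277 |
| 30 Sep 2019 | 150 | 21 Feb 2021 | 22 May 2021 | 247 |

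No row reaches day 360 by 31 October 2020. Working back, 31 October 2020 minus 360 days is 6 November 2019. Enrolment would have to finish at most 97 days (3.2 months) after a 1 August start, against 4-5 months planned.

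**Step 3: how many participants are affected.** Assume uniform accrual and Figure 3's August start. With D the days from S to 31 October 2020, the share below day 360 is 1 - (D - 360)/R.

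- 1 August, R = 120: 1 - 97/120 = 19.2%
- 1 August, R = 150: 1 - 97/150 = 35.3%
- 31 August, R = 120: 1 - 67/120 = 44.2%
- 31 August, R = 150: 1 - 67/150 = 55.3%

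Of the 300 planned, that is about 57 to 166 people. In all four cases the last enrolee is past day 270, so every VL window has opened. At most 7/120 = 5.8% of windows have closed.

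**Step 4: the 18 months.** Counted from S, 540 days end between 22 January and 23 March 2021. That is 83 to 143 days (2.8 to 4.8 months) after 31 October 2020. The last enrolee is then at day 540 - 120 = 420 or 540 - 150 = 390, so everyone has passed day 360. Closing the last window takes 4-5 + 15 = 19-20 months, 1-2 months more than 18.

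**The case against.** The strongest reply is that no endpoint depends on Figure 3. All are defined from enrolment, and section 12.1 takes follow-up data from routine records and the viral load platform, so a VL drawn after October 2020 remains retrievable. Section 5.1 also plans active alignment of sampling: "To synchronize routine VL monitoring and study VL monitoring, study staff will help ensure each site has the capacity to collect these samples". A VL counts from month 9. The calendar is worded as an expectation, and the sentence giving the 18 months starts from recruitment, which on that reading is long enough for everyone's month 12.

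Most of this stands, and it limits the point. It does not remove the contradiction between Figure 3 and the text beside it, and the month-9 opening does nothing for the SAE endpoint, which has no window.

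Three stronger readings are tempting but unsupported:

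- **That 19-55% of primary outcomes would be lost.** That share is people below day 360, not missing VLs. Nothing makes October 2020 a data cut-off, and the documents do not say when in the window VLs are drawn, so the loss cannot be derived.
- **That the 18 months are themselves too short.** Read from recruitment start they cover month 12, and the 1-2 month gap to window closure is small against an approximate figure.
- **That the 18 months were counted from the May 2019 pilot.** This would end between 22 October and 21 November 2020, close to Figure 3, but no section says so.

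**Conclusion.** The inconsistency is real and minor. Under every combination of the stated start and recruitment length, the last month 12 falls after Figure 3's end date, by 23 days at least (23 November 2020) and 113 days at most (21 February 2021).

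The effect on results is conditional on October 2020 being used to close data capture. In that case SAE follow-up would be incomplete for the 19-55% in Step 3, given uniform accrual and an August start, and the VL window would be cut short for nearly everyone. One qualification applies to the VL windows: with the latest start in the text (30 September) and 5 months of recruitment, the last enrolee is only at day 247 on 31 October 2020, so some windows would not yet have opened.

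Any loss would fall in both arms. Nothing here shows a differential bias, and the endpoint definition is not in question.

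**What to change.** 1. In Figure 3, move the end of the trial to no earlier than the last participant's month 12. That is 16-17 months after recruitment start, late November 2020 to February 2021, with analysis after it.
2. In section 16 and the synopsis, state that the 18 months are counted from first enrolment.
3. In the protocol, or in the separate analysis plan that section 11.2 announces, state that primary-endpoint VLs are extracted from routine records up to day 450 after the last enrolment (19-20 months from recruitment start). The plan was not available, so it may already say this.

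The cost is a few wording changes and later extraction and reporting than Figure 3 shows. For the day-450 extraction the delay after 31 October 2020 is 113 to 173 days (3.8-5.8 months) with an August start, and up to 203 days (6.8 months) with a late-September start. Peer-educator stipends may run on if the 12-month questionnaires do. No extra participants or study-specific blood draws are needed.
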